Intervention Procedures: After target enrollment (n=240) is reached, YMCSM Peers will begin the intervention by posting materials according to the timeline developed in the ongoing E-PrEP content project. We will hold weekly project meetings (on different days) with Peers assigned to both E-PrEP and BxNow to ensure appropriate implementation, and to discuss logistical, ethical, or other issues that arise. For participants in the BxNow control arm, Peers will post about general health topics unrelated to HIV or sexual health (e.g. fitness, nutrition, smoking). If a control participant posts a question about PrEP, Peers will refer the individual to the CDC PrEP information site or answer the question privately. Content for both arms will be posted over a 6 week period, and outcome data will be collected via online surveys at baseline, 6, and 12 weeks and after 36 weeks (Table 13). Participants will be given \$20, \$30, and \$40 and 20 online gift-cards or through a Clincard as incentives after completion of assessments at T1, T2, and T3, and T4 respectively.

Anticipated components of E-PrEP: Potential components are listed in Table 2. *However, the exact contents, formats, and mode and timing of delivery of E-PrEP will be informed by input from Peers.*¹²³ We have successfully used this approach in *theSEXword* pilot, with ongoing engagement by participants. We will develop all components for both E-PrEP and the control condition (BxNow), and will also create an intervention activity guide for all 6 weeks, but the exact timeline for intervention delivery will be determined based on findings from Aims 1 and 2. We will thus standardize E-PrEP in its mode of delivery, types of digital media and contents, message framing, and sequence of topics posted and discussed, but Peers will tailor the exact language of posts based on their communication style. Components will be interactive wherever possible; for example, to target a factor such as perceived low risk, participants might assess their risk in an interactive poll, see results in real-time, compare themselves to others, and be engaged by Peers in discussions about risk. To address barriers to access, we might develop a brief time-elapsd video showing where and how to register at a clinic to obtain PrEP. All materials, including assessments, will be smartphone friendly, as most participants use mobile devices.

Table 1. Intervention Timeline

Component	Week	-4	0	6	12	36+
Participant Recruitment						

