Baseline Survey T1						
Exposure to Intervention						
Assessment T2 (intervention end)						
Assesment T3 (Post-intervention)						
Assesment T4 (Follow-Up)						

Developing BxNow (control condition): BxNow will focus on general health topics unrelated to HIV or sexual health (i.e. fitness, nutrition, smoking), but will also include basic information on PrEP as well as referral resources. We will develop a 6-week timeline to match the E-PrEP timeline, and we will compile publicly available digital media addressing general health topics (e.g. from CDC LGBT website). As with E-PrEP, standardized BxNow content will be delivered by Peers, using their own language. Additionally, after trial end (12 weeks), BxNow participants will be exposed to all E-PrEP components.

Setup of intervention sites: We will provide customized training and setup to the project team (PI, RA, Peers), establish 'E-PrEP' and 'BxNow' (control) private virtual communities (e.g closed Facebook group, private Twitter feed, private Tumbler blog), and implement systems for recruitment, consent, and online data collection (e.g. # of sites joined by each participant, engagement indicators for each posted component and for each participant, and other process measures).

Risk: Possible risks faced by the participant include: confidentiality issues, inconvenience and discomfort associated with interviews, potential risk compensation if PrEP is adopted, and fear that refusal to participate will affect relationship with Peers. More detail information about the potential risk and precautions against those risks can be found in the attached Protection of Human Subjects document sections I.4 and I.5.

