Compensation: Participants will be given \$20, \$30, and \$40 and \$20 as incentives after completion of assessments at baseline (T1), 6 weeks (T2), and 12 weeks(T3), and post 36 weeks (T4) (respectively). The participants will be given the choice to receive their incentives either via e-codes, Amazon online-gift cards, or by receiving a Clincard.

Data Collection:

We will collect three general types of data: 1) online processes (e.g. referral source, # of platforms joined by each participant); 2) measures of engagement with intervention components (e.g. # of views, time spent online); and 3) measures of outcome and independent variables, collected through online surveys at the ~~four~~three time points (see Table 2). To help assess both degree of exposure to intervention components and possible contamination between the two conditions, the surveys at 6 weeks (T2), ~~and~~ 12 weeks (T3) will display random samples of study and non-study graphics and posts and ask participants if they recall seeing them, with E-PrEP materials embedded in the choices.^{106,119,141}

Table 2. Data Collection					
Measures	Week	0	6	12	36+
PrEP intention, use, knowledge, attitudes		x	x	x	x
Perceived PrEP attributes		x	x	x	
HIV testing, risk behaviors		x	x	x	
Peer affinity and network data		x	x	x	

Table 2. Data Collection					
Measures	Week	0	6	12	36+
PrEP intention, use, knowledge, attitudes		x	x	x	x
Perceived PrEP attributes		x	x	x	
HIV testing, risk behaviors		x	x	x	
Peer affinity and network data		x	x	x	
Sociodemographic Factors		x			
Sexual Orientation		x			
Healthcare access		x	x	x	
Substance use		x	x	x	
Perceived risk, stigma		x	x	x	
Social media engagement		x	x		
Intervention exposure			x	x	

Data Security:

In order to securing information over the Internet and social media, and protecting participant data, an electronic, password protected and encrypted system will be developed to store analyses, and social media activity will remain private to study participants.¹⁶⁴ Research participants will be informed of how communications are recorded and stored during the online informed consent process. Due to the ever-changing and evolving nature of privacy issues on social media sites, we will review privacy settings for all social media study sites at least every four weeks and adjustments will be made to the study sites as necessary.

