Potential side effects from PrEP if adopted: This trial is not providing PrEP directly to participants, but rather, as one component, linking participants to routine comprehensive primary care health centers where they could obtain/be prescribed PrEP. Like any medication therapy, there are potential side-effects related to using the medication. Side effects related to current oral PrEP (emtricitabine-tenofovir) have been reported to be minimal with no major risks or warnings identified currently. While it is the prescribing providers' responsibility to monitor the patient for potential side-effects, we will also monitor for potential side-effects among participants who report using PrEP. At each assessment during the trial and during the follow-up (0, 6, 12 weeks), we will ask questions to elicit information about potential side effects for those participants indicating that they have started using PrEP and to solicit information about if the participant is having adequate follow-up and lab monitoring (e.g. obtaining labs to monitor renal function, getting regular HIV testing, etc.). The online assessment will have pre-programmed prompts for those PrEP users reporting inadequate monitoring and will provide brief education on PrEP monitoring and inform them to follow-up with their provider to obtain monitoring labs and/or testing.

I.5. Adequacy of protection against risks

We will follow procedures as outlined by the National Institute of Mental Health (NIMH) Internet-based Research Interventions: Suggestions for Minimizing Risk (2007) and other evolving best practices in ethical conduct of social media and Internet research.^{95,135,153-163} We will additionally work with our social media consultants to ensure technical capacity of maintaining ongoing security and privacy. Peers will also not have direct access to raw or un-summarized data to protect confidentiality of participants.

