11. **Side Effect Management:** While it is the prescribing providers' responsibility to monitor the patient for potential side-effects, we will also monitor for potential side-effects among participants who report using PrEP. At each assessment during the trial and during the follow-up (0, 6, 12 weeks), we will ask questions to elicit information about potential side effects for those participants indicating that they have started using PrEP and to solicit information about if the participant is having adequate follow-up and lab monitoring (e.g. obtaining labs to monitor renal function, getting regular HIV testing, etc.). The online assessment will have pre-programmed prompts for those PrEP users reporting inadequate monitoring and will provide brief education on PrEP monitoring and inform them to follow-up with their provider to obtain monitoring labs and/or testing.

I.6.Potential benefits to subjects and others. The potential benefit to participants in this study could be linkage-to-care, access to HIV/STI prevention and testing services otherwise difficult to obtain, and access to credible information on new and existing HIV prevention tools. But all participants may not realize these benefits and there will be no other direct benefits to participants. However, if effective, E-PrEP could be implemented broadly and rapidly diffuse information on available HIV prevention tools and improve linkage to HIV prevention and treatment services for YMCSM, a hard-to-reach population. Additionally, E-PrEP could have significant public health benefit by reducing the HIV burden in YMCSM and the broader population.

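### PrEP side-effect and lab-monitoring questions are listed only for weeks 0, 6 and 12, so a participant who reports PrEP use in the survey after 36 weeks (T4) is not asked them

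*Combined protocol and SAP*

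**What the plan says.** The safety commitment appears twice in near-identical words, in I.4 (potential side effects from PrEP) and in I.5 item 11 (Side Effect Management): "At each assessment during the trial and during the follow-up (0, 6, 12 weeks), we will ask questions to elicit information about potential side effects". It applies to participants who say they have started PrEP, and it extends to whether they are getting adequate follow-up, renal labs and regular HIV testing. A further sentence attaches an action to the answers: "The online assessment will have pre-programmed prompts for those PrEP users reporting inadequate monitoring". Those users are shown brief education and told to return to their provider.

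The survey schedule is set in Intervention Procedures: "outcome data will be collected via online surveys at baseline, 6, and 12 weeks and after 36 weeks". Table 1 (Intervention Timeline) names the last one "Assesment T4 (Follow-Up", and the Compensation paragraph pays for it. In Table 2 (Data Collection), the row "PrEP intention, use, knowledge, attitudes" is marked at weeks 0, 6, 12 and 36+.

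On the control arm, the paragraph on developing BxNow says that "after trial end (12 weeks), BxNow participants will be exposed to all E-PrEP components". Before that, BxNow content "will also include basic information on PrEP as well as referral resources".

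**The concern.** The plan asks about PrEP use four times but lists the accompanying safety questions three times. The survey left out is T4. Someone who reports PrEP use at week 6 or 12 is asked about side effects and laboratory monitoring and, if monitoring is inadequate, is told to go back to the provider. Someone who gives the same answer at T4 is not asked and gets no prompt.

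T4 is the only survey that can identify anyone, in either arm, who starts PrEP after week 12. That includes controls who act on the E-PrEP content they receive at that point. What is at stake is a small participant-safety benefit, not the trial's inference. The data and safety monitoring plan (I.10) refers back to the same side-effect text, so the omission carries into it.

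**Working it through.** The plan gives no figure to reproduce. The check sets the schedules side by side.

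**Surveys and what they ask**

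| Survey | PrEP use asked (Table 2) | Side-effect and lab questions listed (I.4, I.5 item 11) |
|---|---|---|
| T1, week 0 | yes | yes |
| T2, week 6 | yes | yes |
| T3, week 12 | yes | yes |
| T4, week 36+ | yes | no |

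**Waves that can find new users.** The exclusion criteria remove people already taking PrEP, so week 0 should yield almost no side-effect reports. New users can appear at weeks 6, 12 and 36+, which is 3 waves. The safety questions are listed at 2 of them, so 3 − 2 = 1 wave, T4, is without them.

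**Does anything else in T4 cover the ground?** Table 2 has 11 distinct rows. Eight are marked at week 12 and one at 36+. The row on HIV testing and risk behaviours is not marked at 36+, so T4 does not collect HIV testing by another route. No row covers side effects or laboratory monitoring at any week. Table 2 therefore cannot show on its own whether those items appear in a given survey, and the lists in I.4 and I.5 are the only schedule they have.

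**What follow-up means in the human-subjects section.** I.5 item 7 describes a 6-week intervention period and a 6-week post-intervention follow-up: 6 + 6 = 12 weeks. I.6 places the end of follow-up, and the final survey, at 12 weeks. The Fairness row of I.8 does the same. So the listed weeks are the complete set for that section, and omission at T4 is the natural reading of "during the follow-up (0, 6, 12 weeks".

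**Was that section written with T4 in view?** Only in part. The activities and compensation table in I.1 lists three time points (0, 6 and 12 weeks) beside four payments (20, 30, 40 and 20 dollars). I.2 gives three survey times, and I.5 item 5 gives a duration of 12 weeks. The pattern suggests that T4 was added to the main protocol without a full update of this section.

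**Other routes after week 12.** I.6 offers both arms linkage-to-care coordinators, I.8 keeps the team available to controls, and I.10 has investigators monitor regularly and summarise adverse events every 4 weeks and at study end. None of these asks PrEP users at T4 about side effects or labs.

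**The case against.** The strongest case against is that no promise is broken. The sentence carries its own list of weeks, and its section consistently ends follow-up at week 12, so each assessment there means weeks 0, 6 and 12. The wider reading leans on a timeline label elsewhere, and the main protocol itself calls week 12 the trial end. On this view the point is one symptom of incomplete editing, and a short late survey may be intended.

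Much of that stands. A reader might infer that the plan contradicts its own commitment at T4. The documents do not support that, because within its section the sentence is consistent. Nor do they show whether the omission was an oversight or a choice. But consistency within the section does not help the participant: it confirms that T4 is left out, although T4 asks the question that identifies PrEP users.

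A reader might also infer that PrEP users go unmonitored from week 12 onward. That is not supported either. The trial does not supply PrEP, I.5 item 11 assigns monitoring to the prescriber, and the linkage and contact routes continue. Nor does week 12 mark the controls' first contact with PrEP information, since they receive basic information and referrals earlier.

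**Conclusion.** The point holds as a cheap safety improvement. As listed, the side-effect and monitoring questions and the dependent prompt stop at week 12, while PrEP use is asked again at T4. One of the three waves at which new users can be found has no safety questions.

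The impact is small. The Analytic Plan expects little actual PrEP use, prescribers carry the monitoring duty, and linkage stays open. The documents give no basis for estimating how many users T4 would find or how many of them would be poorly monitored. Sample size, power and all outcome analyses are unaffected. The conclusion assumes that the listed weeks would be followed as written when the T4 survey is programmed.

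**What to change.** Add 36+ weeks to the lists in I.4 and I.5 item 11. At T4, show the existing conditional side-effect and monitoring items, and the existing prompt, to participants who report PrEP use. Add a Table 2 row for these items, marked at 0, 6, 12 and 36+, so that the schedule is visible in one place.

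The cost is a slightly longer T4 survey for PrEP users only; the items and prompt are already planned for the earlier surveys, and no visit or extra staff is needed. The gain is limited to a single retrospective check at least 36 − 12 = 24 weeks after T3. It does not provide monitoring in the interval.

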Online Safety Monitoring Plan: Study personnel (Peers, Research Assistant, and PI) will monitor all social media site communications and facilitate immediate response to possible behaviors that may characterize a participant as having an increased risk of self-harm or deterioration. All participants will be informed that necessary actions will be taken in the event of an emergency or potential risk as defined by the research team. The peers and the research assistant will be trained to scan and read ALL postings on Study profiles they are responsible for, including written messages, photos and videos, on all social media sites they are managing and an active part of. Each week, the peers will report to the research assistant, who will in turn report to the PI, on the content of the postings and any significant postings related to the E-PrEP intervention. These reports will include any alarming posts that may indicate or allude to self-harm or other unsafe activities. If a participant is suspected of self-harm or engaging in unsafe activities, the research team will make all efforts to reach out to the concerned participants via the social media site and refer them to appropriate resources to the extent possible online and through the YMSM linkage-to-care coordinators at the Adolescent AIDS Program and Montefiore Medical Center's Primary Care HIV program. In addition, a resource guide that outlines and details unsafe activities and implications of risky behaviors and self-harm will be updated by the research team for the Peers to use to identify individuals in need. This resource guide will include detailed contact information of physical and virtual resources that will appropriately address the needs of such individuals. Every effort will be made to engage a participant in the care that he needs in the event of an emergency or possible risk. These efforts include, but are not limited to, calling the peers, contacting social media site friends, contacting professionals to intervene across the site and referring the participant to offline clinical sources.

I.11. Additional Online Safety and Suicidal ideation protocol

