Given that we cannot actually verify real-world identities of participants and will not be collecting residential address/location information (to encourage participation and help minimize perceived breaches of privacy), the following protocol will allow us to monitor and address safety concerns of participants in a timely manner to the extent possible. While our study poses no more than minimal risks, and we do not anticipate encountering such safety concerns listed below (based on our prior experiences implementing similar studies, discussing with other researchers conducting social media based interventions), these measures and protocols will be in place to maintain adequate protection of participants in the event they are needed.

1. Study Team (PI, research assistant, Peers) sees status update display on study social media sites or receives email, phone calls that suggest suicidal ideation. Key words may include "kill myself," "end it all," "not be around anymore," "better off dead" or themes alluding to these concepts. Also includes any description of an intended activity linked to suicide such as "I'm going to jump off a bridge," "I'm going to shoot myself."
 - a. Research Assistant and/or Peer notes date and time of reference
 - i. Write down name and any available contact information for that profile owner on a document separate from the data collection sheet for this study.
 1. If reference is within the last 7 days, call [name] immediately. If for some reason he is not reachable by cell phone, home phone or pager within 2 hours, call the IRB.
 2. If reference is older than 7 days but no status updates since, call [name] immediately.
 3. If reference is older than 7 days, read status updates since and note any references to "feeling better" or similar comments. If these are present, discuss with [name] the next day during business hours.
2. Protocol for acute Suicidal Ideation noted on profiles (within last 7 days)
 - a. [name] will perform status check on profile owner. Profile owner will be called using the phone listed on the Social Media profile if available or direct messaged, or through any other collected locator information. If the participant is connected to a Peer, the Peer will be notified as they may have other methods of reaching this individual. If participant is not reachable within one hour, we will call 911 to notify of suspected suicidal ideation. This protocol will be made known to participants during the informed consent.

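### In the visible text of I.11, the 2-hour wait that ends at the IRB is not tied to the one-hour 911 limit for the same acute posts, and no one is assigned the status check if the named person is not reached

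*Combined protocol and SAP*

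**What the plan says.** Section I.11 of the combined protocol and SAP sets out the response to suicidal content. Item 1 opens with its trigger, "Study Team (PI, research assistant, Peers) sees status update display on study social media sites", and extends it to emails and phone calls. The research assistant or a Peer records the reference. If it dates from the last 7 days, item 1.a.i.1 has them call one named person (name masked) at once, and continues: "If for some reason he is not reachable by cell phone, home phone or pager within 2 hours, call the IRB".

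Item 2 has its own heading, which begins "Protocol for acute Suicidal Ideation noted on profiles (within last 7 days", so it covers the same posts. Under item 2.a a named individual (also masked) "will perform status check on profile owner", by phone, direct message or other locator details; a connected Peer is told as well. Then: "If participant is not reachable within one hour, we will call 911 to notify of suspected suicidal ideation". The item ends: "This protocol will be made known to participants during the informed consent".

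Other text that bears on the point:

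- The opening of I.11 says the study "will not be collecting residential address/location information" and that safety concerns of this kind are not anticipated.
- The Online Safety Monitoring Plan has Peers, research assistant and PI watch the sites and "facilitate immediate response to possible behaviors that may characterize a participant as having an increased risk of self-harm or deterioration". It allows professionals to be brought in.
- I.5 item 5 lets Peers or the research assistant refer and intervene under a resource guide. I.5 item 6 says the guide's procedures include calling the police.
- Elsewhere the IRB receives reports (I.10: serious events and deaths within 48 hours, unanticipated non-serious events within 30 days) or is a contact through which participants can verify the study's approval (I.5 item 4).

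**The concern.** The two items govern the same event but do not refer to each other. Item 1.a.i.1 tolerates up to two hours of failure to reach the study's own contact. Item 2.a tolerates one hour of failure to reach the participant. The text does not say whether the second clock runs while the first is open.

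The end point of the first branch is also a problem. Someone who follows item 1.a.i.1 literally finishes at the IRB, which is given no task of checking on the participant or calling for help. At that point no assigned person has made contact. Those most likely to see a post are the research assistant and the Peers, and the training section describes the Peers as lay community members. They should not have to work out for themselves that item 2 applies regardless of item 1.

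What is at stake is how quickly a participant who may be in danger is checked on, and how quickly emergency services are told.

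**Working it through.** The plan states no total time from detection to the 911 call, so there is no figure to reproduce. The check adds the two stated limits under each reading the text allows.

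**Inputs**

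- Limit for reaching the named person: 2 h (item 1.a.i.1).
- Limit for reaching the participant before 911: 1 h (item 2.a).
- Start of the 1 h: not stated.
- Who does the status check if the named individual is not reached: not stated in I.11.
- Who calls 911: given only in the first person plural. Item 1 lists the Study Team as PI, research assistant and Peers, so any of them could be meant.

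**Assumptions.** Calls to the named person begin at detection. Items 1.a.i.1 and 2.a mean the same person. The status check begins as soon as someone takes it on. Let *t* be the hours from detection until the named person is reached.

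| Reading | Formula | Detection to 911 |
|---|---|---|
| A. Hour starts at detection; any team member may call | 1 | 1 h |
| B. Hour starts at the status check; named person reached at *t*, 0 ≤ *t* ≤ 2 | *t* + 1 | 0 + 1 = 1 h to 2 + 1 = 3 h |
| C1. Hour starts at the status check; not reached; a colleague takes over at 2 h | 2 + 1 | 3 h |
| C2. Hour starts at the status check; not reached; no one takes over | none | no stated time |

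**With the hour run from detection and a backup assigned:** 1 h on every reading. The gain is:

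- A: 1 − 1 = 0 h
- B: (*t* + 1) − 1 = *t*, so 0 to 2 h
- C1: 3 − 1 = 2 h
- C2: cannot be calculated; a stated time replaces none

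Reading A has its own weakness. The 911 call at 1 h falls before the 2 h limit has run out, so it can be made with the only person assigned to the check not yet reached. A backup therefore helps there too, although no time is gained.

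**Do other sections close the gap?** The Online Safety Monitoring Plan and I.5 items 5 and 6 allow Peers and the research assistant to respond. None sets a time limit or assigns a person for the case where the named individual is not reached, and none links the two clocks.

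**The case against.** The case on the other side has four parts.

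- **The 2 hours is not a holding period.** Item 1.a.i.1 says to call at once, and the 2 hours only fixes when failure to reach that person goes to the IRB. Nothing tells staff to suspend other action. A reader might infer that the plan orders a two-hour pause before anyone acts. The documents do not support that: item 2 stands on its own, its 911 sentence speaks for the team, and the monitoring plan asks for an immediate response. This stands, and it is why reading A, with no time gained, must be kept.
- **Others may already act.** A reader might infer that the study has no backup. That goes too far. The resource guide is not reproduced, contact details are not visible, and other sections let Peers and the research assistant intervene. Only the visible I.11 text can be said to assign no one. What remains is that I.11 points to no backup for this branch.
- **Names are masked.** If the two items mean different people, readings B and C lose their basis. Item 1 would still not say how item 2 is started when the first person is unreachable.
- **Events are unlikely and 911 may achieve little.** The documents give no frequency and do not anticipate such events, and without an address a call may not lead to the participant. Both limit the benefit. Neither is a reason to leave the rule unclear in the one situation it was written for.

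**Conclusion.** The point holds as a participant-safety gap in the wording of I.11. It should be fixed, and confidence is moderate. Two instructions for the same acute posts are unlinked: one ends at a body with no described response role, and the other has no stated start for its hour and no deputy for its status check. Detection to 911 is 1 h on the most favourable reading, up to 3 h if the hour starts at the status check and the named person is reached late, and unstated if he is never reached and no one takes over.

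The 3 h figure should not be read as the expected delay. It needs an acute post, late or failed contact, an hour that starts at the status check, the same person in both items, and no one acting earlier under the other sections. Nor does the point touch the trial's findings: no estimand, analysis or result is affected.

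**What to change.** **In item 1.a.i.1**, replace the 2-hour wait and IRB fallback with an assigned existing team member, for example the research assistant. That person starts the item 2.a status check if the named person does not answer the first round of calls, and in any case well inside the hour. Notify the IRB in parallel.

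**In item 2.a**, state that the one-hour limit runs from detection of the post and that the assigned team member may make the 911 call.

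Update Peer and staff training and the consent wording, since participants are told of this procedure there. If the resource guide already names a backup, cite it in I.11.

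The cost is short wording changes, training and a backup duty for someone already on the team. The trade-off is time for the check: if it starts *h* hours after detection, 1 − *h* hours remain before the 911 call. Some calls may then concern posts that a longer check would have cleared. That carries a confidentiality cost in a population for which I.4 lists breach of confidentiality and outing among the primary risks. A prompt handover keeps *h* small and limits this.
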